
Individuals diagnosed with MDD.
	
 1) Males or females 18-65 years of age; 2) Meeting clinical diagnostic criteria for MDD according to the fifth edition of the Diagnostic and Statistical Manual of Mental Disorders (DSM-V); 3) Having depressive symptom scores > 14 on the Patient Health Questionnaire-9 (PHQ-9 > 14); 4) Having third-party insurance payers and meeting Insurer's criteria for payment of at least 20 sessions of TMS Depression treatments; 5) If patient is currently receiving other psychotropic medication treatment, having been stable on that treatment for at least 8 weeks; 6) Able to provide written informed consent and able to read English. 	
 1) Patients with a diagnostic history of bipolar disorder, schizophrenia or schizoaffective disorder or currently exhibiting psychotic features; 2) Serious, active suicidal risk as assessed by evaluating psychiatrist. Serious active suicidal risk is reflected by patient having a plan and intent to end his or her life. History of suicidality in itself is not an exclusion; 3) Except for Mild or Moderate Alcohol Use Disorder according to DSM-V criteria, having any other substance use disorder during the 3 months prior to screening; 4) Any history or signs of serious medical or neurological illness including a) seizure disorders, b) structural brain damage due to a penetrating head injury, or c) structural and/or functional brain damage due to stroke. Except for seizures, patients with a clinical abnormality may be included only if the study clinician considers the illness will not introduce additional risk and will not interfere with the study procedures; 5) Females will be excluded if they are pregnant (i.e. positive pregnancy test identified after their intake at the treatment clinic); 6) Recent history (e.g. within the past two years) of traumatic brain injury (TBI) with loss of consciousness for 20 minutes or more; 7) Any history or signs of metal objects (e.g. surgical clips, cardiac pacemakers, metal implants, etc.) in the body at the time of screening. MRI can have risks

for persons with foreign bodies implanted in their body.

Item 6

Research Plan / Description of the Research Methods a. Provide a comprehensive narrative describing the research methods.

Provide the plan for data analysis (include as applicable the sample size calculation).

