Subjects will be recruited at their treatment clinic from that institution's MDD out-patient program by the study staff supervised by the Site-Principal Investigator's team. Upon admission to their treatment clinic, subjects will be informed about this treatment trial by either their staff psychiatrist or a member of the treatment clinic's research team. Each subject will be given an information sheet describing the study. If interested in participating, each subject will be shown a video describing the treatment trial and each of the tools/treatments used throughout the study (i.e. MRI and TMS).

As part of the treatment clinic's standard of care assessments, potential subjects will be asked to complete the following assessment at the subject's treatment clinic:

Patient Health Questionnaire-9 (PHQ-9; Kroenke, Spitzer, & Williams, 2001). The PHQ-9 is a widely used and well-validated instrument for measuring the severity of depressive symptoms. It consists of 9 items that assess both affective and somatic symptoms related to depression and depressive disorders; these 9 items correspond to the DSM diagnostic criteria for Major Depressive Disorder (MDD). Respondents rate the frequency with which they have been bothered by depressive symptoms within the past two weeks on a scale ranging from 0 ("not at all") to 3 ("nearly every day"). Scores on all items are summed to obtain a total severity score. Scores reflect no significant depressive symptoms (0-4), mild depressive symptoms (5-9), moderate depressive symptoms (10-14), moderately severe depressive symptoms (15-19), and severe depressive symptoms (>19). Respondents also indicate the degree to which their depressive symptoms have made it difficult for them to do their work, take care of things at home, or get along with other people, from "not difficult at all" to "extremely difficult." The PHQ-9 has high internal consistency (e.g., alpha ranging from .83 to .92; Cameron, Crawford, Lawton, & Reid, 2008), and correlates strongly with other measures of depression (Kroenke et al., 2001).

Results from this assessment may be used to assess each patient's inclusion/exclusion criteria and as the PHQ-9 baseline assessment for the patient.

Pre-Screening at Treatment Clinic Intake

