Once the subject has completed the psychological assessments required to determine inclusion/exclusion criteria at the subject's treatment clinic, eligible participants will then schedule an appointment at the RII to proceed with the study. An authorized and trained member of the research team will engage the potential participant in an interactive explanation of the study guided by the informed consent document (ICD). After the participant has read the ICD, he or she will be given the opportunity to consider participation and discuss the research with family and friends. Once the potential participant has reached a decision, the advising staff member will review the purpose of study, duration of study, study procedures, the experimental components of the study, the potential risks and discomforts, the potential benefits, any alternatives to participation, protection of participant's confidentiality, and the contact information for both the researchers and the regulatory bodies overseeing the conduct of the study with the participant to ensure the participant has an understanding of the study. If the individual is agreeable to participation the advising staff member will then have the individual sign the consent form in the presence of a witness. A copy of the signed ICD will be given to the participant for their reference. Over the course of the study, the Research Team will be available to answer any questions about the research. Following consent, the participant meets regularly with the research staff. Ongoing discussions occur to ensure the participant's questions and concerns are addressed during the course of the study. Potential participants will have the study explained to them in a safe and private location before any assessments are conducted.

Phase I: Baseline Assessment at the RII. When the participant arrives for their appointment at the RII and has signed the ICD, the participant will undergo a review of the metal screening history and will complete the PHQ-9 and the Montgomery and Asberg Depression Rating Scale (MADRS). The MADRS is a standardized clinical assessment instrument to ascertain depressed mood and neurovegetative signs and symptoms of depression. These assessments will be performed by a trained member of the RII's research team.

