Random Assignment. Prior to the TMS Treatment Phase, participants will be randomly assigned by a member of the RII's research team (using a statistically generated randomization program) to 1 of 3 active irTMS treatment arms. An irTMS treatment plan will be developed specifically for each participant, which will be securely-transmitted to the irTMS treatment team at the subject's treatment clinic. The master list of treatment arm enrollment will be securely-stored (i.e. password-encrypted) on UTHSCSA's XNAT server and will not be available to members of the research team until all of the participant's treatment sessions and symptom assessments have been completed. Therefore, all members of the subject's treatment clinic's irTMS treatment team will be blinded to which treatment arm each participant is assigned. irTMS treatment visits will take place at the subject's treatment clinic within two week's after the Baseline scan and development of the treatment plan. This ensures that the subject's scores on the PHQ-9 and the MADRS reflect their current state of depression.

Phase II: TMS Treatment Phase.

irTMS Treatment Planning. All irTMS treatments will be planned for robotic, image-guided irTMS delivery—which will be performed at their treatment clinic. The acquired MRI images will be used to compute a subject-specific, treatment plan, which will be stored and used during their respective irTMS session at their treatment clinic. Image guidance will be based on treatment plans developed from high-resolution structural MRI and resting-state BOLD fMRI acquired at the RII. From the T1-weighted MRI (described above), two surface models are computed: a model of the scalp surface, for use in registration of the subject to the treatment plan; and, a model of the cortical surface including cortical surface normals. Both models are created using a modification of the dividing cubes algorithm following automated tissue segmentation. The scalp surface

model is based on the air-scalp interface, which is readily obtained by simple thresholding. The cortical surface model is based on pre-classification of brain tissue into gray, white and CSF surfaces, using the FMRIB's Automated Segmentation Tool.

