Clinical Outcomes Data Analysis plan. All pre-treatment and post-treatment MRIs will be acquired and analyzed at the RII, however, all of the statistical analysis of the symptom scores for this project will be done upon completion of recruitment and termination group blinding. The primary efficacy outcome measure will be the PHQ-9 for MDD symptoms assessed pre-treatment, weekly during treatment, post-treatment, and 1/3-months following the completion of treatment and the MADRS for the diagnosis of MDD assessed pre-treatment, post-treatment, and 1/3-months following the completion of treatment. The primary analysis will use

mixed effects regression models. Secondary analysis will focus on changes in MDD symptoms clusters, effects of the intervention in mood symptoms, functioning and cognitive outcomes. Types and rates of adverse events will be summarized and compared across the study groups. The durability of benefit and the clinical significance of PHQ-9 changes will be explored. Non-compliance to protocol as defined as missing three consecutive irTMS sessions or receiving less than 10 irTMS sessions during treatment at their treatment clinic will be assessed for and evaluated in data analysis.

Discontinuation of Subjects. Subjects may be discontinued from study treatment and assessments at any time. Specific reasons for discontinuing a subject from this study are: 1) Voluntary discontinuation by the subject, who is at any time free to discontinue his/her participation in the study without prejudice to further treatment; 2) Clinical deterioration: The following are objective criteria for clinical deterioration, a 25% increase in the PHQ-9 at any time during the study and/or the onset of active suicidality as assessed by the study clinicians requiring treatment outside of the study protocol; 3) Evidence of intolerable adverse reaction, or unable to tolerate irTMS or MRI; 4) Non-compliance to protocol by missing three consecutive irTMS sessions or as judged by the investigator; 5) Safety reasons as judged by the investigator.

Item 7 Risks Section:

Complete the following table to describe the risks of all **research procedures** listed in Step 2, Institutional Form (items 28-34). *Do not list risks of Routine care procedures here.*

N/A, Risks are described in the informed consent document – do not complete this table.

Research procedures

example:

- History and physical
- Questionnaire
- Laboratory tests

Add or delete rows as needed

Risks

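### The plan allows the clinic-intake PHQ-9 that selects patients to serve also as their baseline, although the PHQ-9 is repeated at the RII; this can overstate within-arm improvement and mix baselines, without biasing the randomised comparisons.

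*Combined protocol and SAP*

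**What the plan says.** Item 5 sets the entry threshold: "Having depressive symptom scores > 14 on the Patient Health Questionnaire-9 (PHQ-9 > 14"). Item 6, Recruitment, describes a PHQ-9 completed at the treatment clinic as part of standard care and says that its results may serve both to judge eligibility and "as the PHQ-9 baseline assessment for the patient".

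Item 6, Consent Process, shows that eligibility is settled at the clinic: "Once the subject has completed the psychological assessments required to determine inclusion/exclusion criteria at the subject's treatment clinic, eligible participants" then book the RII visit. Under Phase I: Baseline Assessment at the RII, each participant who has signed consent "will complete the PHQ-9 and the Montgomery and Asberg Depression Rating Scale (MADRS"). The baseline MRI follows at the same visit.

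Item 6, Random Assignment, places allocation after that visit: "Prior to the TMS Treatment Phase, participants will be randomly assigned". It also requires treatment to begin within two weeks of the baseline scan, so that "scores on the PHQ-9 and the MADRS reflect their current state of depression".

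The Table of Study Procedures, as extracted, marks the pre-study PHQ-9 under Baseline and not under Clinic Intake. The Clinical Outcomes Data Analysis plan names the PHQ-9 as a primary efficacy measure assessed pre-treatment and at later visits, analysed by mixed effects regression. It does not say which pre-treatment score is meant or how baseline enters the model. Discontinuation of Subjects defines clinical deterioration partly as "a 25% increase in the PHQ-9 at any time during the study", with no reference score.

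**The concern.** Each participant has two pre-treatment PHQ-9 scores and the plan has no rule for choosing between them. The intake score is the one on which patients are selected for being high. On average such a score falls on repeat even when nothing has changed, and with the intake score as baseline that fall counts as improvement in every arm.

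The clearest casualties are within-arm PHQ-9 change and the planned exploration of its clinical significance. Because all three arms deliver active stimulation, no sham arm would show how much of the within-arm change is artefact.

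Two further effects are smaller. The wording allows one participant's baseline to be the intake score and another's the RII score, which adds noise to individual change scores. And the interval from intake to the RII visit has no limit, so the intake score may not match the baseline scan in time. That matters for Hypothesis 2b, which correlates connectivity change with symptom improvement, if improvement is measured by the PHQ-9.

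**Working it through.** **The plan's own figures.** The plan gives no figure for this point to reproduce. It states no PHQ-9 SD, no clinic mean and no test-retest correlation. The only reliability given is internal consistency (alpha .83 to .92), which is not a correlation between two occasions.

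**Inputs.**
- From Item 5: PHQ-9 above 14, that is 15 or more, taken as a continuous cut at 14.5.
- Assumed: pre-selection mean μ, SD σ, test-retest correlation r, and no true change between intake and the RII visit.

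**Formula.** With a = (14.5 − μ)/σ and λ(a) = φ(a)/[1 − Φ(a)], the mean intake score of those selected exceeds their mean repeat score by (1 − r) × σ × λ(a).

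**Results with σ = 5.**

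| μ | a | λ(a) | r = 0.7 | r = 0.8 | r = 0.9 |
|---|---|---|---|---|---|
| 14 | 0.1 | 0.863 | 1.29 | 0.86 | 0.43 |
| 16 | −0.3 | 0.617 | 0.93 | 0.62 | 0.31 |
| 18 | −0.7 | 0.412 | 0.62 | 0.41 | 0.21 |

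For example, at μ = 14 and r = 0.7: 0.3 × 5 × 0.863 = 1.29. The range is about 0.2 to 1.3 points.

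**Wider assumptions (μ 12 to 18, σ 4 to 6, r 0.6 to 0.9).**
- Largest: μ = 12, σ = 6, r = 0.6 gives a = 0.417, λ = 1.081, and 0.4 × 6 × 1.081 = 2.59.
- Smallest: μ = 18, σ = 4, r = 0.9 gives a = −0.875, λ = 0.336, and 0.1 × 4 × 0.336 = 0.13.

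**Effect on the analyses.** A simulation used 4,000 replicates of two arms with 50 patients each, μ = 15, σ = 5 and r = 0.8. There was no true change in the control arm and a true arm difference of −2.0. In the mixed case each patient's baseline was chosen at random, half from each source.

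| Baseline used | Control-arm change | ANCOVA arm difference | SD of that difference |
|---|---|---|---|
| Intake | −0.72 | −2.01 | 0.60 |
| RII | −0.005 | −1.99 | 0.58 |
| 50/50 mix | −0.36 | −2.00 | 0.59 |

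The formula gives (1 − 0.8) × 5 × 0.735 = 0.74 for the intake row, in agreement with the simulation. Within-arm change carries the artefact in full with the intake score, by half with the mix, and essentially not at all with the RII score. The arm difference is unbiased in all three cases. The variance ratio of intake to RII is (0.60/0.58)² = 1.07, a small loss of precision.

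**The case against.** The strongest reply is that no primary conclusion is touched. Hypotheses 1a and 1b compare arms, both PHQ-9 scores come before allocation, and selection is the same in every arm. This stands. A reader might infer from the talk of overstated improvement that the efficacy comparison is biased; the design and the simulation do not support that.

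A reader might also infer that regression to the mean distorts Hypothesis 2b and the durability analysis. It need not. A common upward shift in baseline leaves a correlation unchanged, so only noise, mixed baselines or a mismatch in time with the scan could weaken Hypothesis 2b. That hypothesis does not name the PHQ-9 either; improvement could be MADRS change, whose only scheduled pre-treatment assessment is at the RII. Durability can be judged from post-treatment to follow-up without any baseline.

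Third, the RII score appears to be the intended baseline: the Phase I heading, the reason given for the two-week window and the schedule table all point to it. The table's column alignment could be an extraction artefact, but the other two places remain. On this view the fault is one permissive sentence, and mixing is allowed, not certain. That is fair, but the sentence is an explicit permission and nothing in the analysis section overrides it.

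Finally, every magnitude is assumed, and the upper values need a low clinic mean and modest reliability. If the cut were applied again at the RII, that score would carry some regression to the mean too. The pre-screening text mentions further screening after consent, but no section says the PHQ-9 threshold is reapplied.

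**Conclusion.** The point holds as a conflict in the definition of baseline, of moderate weight. The Recruitment section permits a baseline that is selected for being high and has no limit on its age, against the evident intent of the Phase I and Random Assignment sections. If it is used for everyone, within-arm PHQ-9 improvement is overstated by about 0.2 to 1.3 points under the main assumptions, and by about 0.1 to 2.6 under the wider ones. If it is used for some participants only, the overstatement is proportionately smaller. These sizes rest on normal scores and on an assumed mean, SD and test-retest correlation. The randomised contrasts are unbiased and their loss of precision is small.

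**What to change.** 1. In Item 6, Recruitment, delete the clause allowing the intake score to serve "as the PHQ-9 baseline assessment for the patient". Keep the intake PHQ-9 for eligibility only.
2. In the Clinical Outcomes Data Analysis plan, name the PHQ-9 from the RII baseline visit as the single analysis baseline for change scores and model covariates.
3. State how a missing RII baseline score is handled.
4. Make these changes before unblinding, so that the baseline cannot be chosen with results in view.

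Separately, the 25% PHQ-9 deterioration criterion names no reference score, and the two pre-treatment scores would give different thresholds. The sponsor should reconcile Discontinuation of Subjects with the Recruitment and Phase I sections. No reference value is proposed here.

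The cost is wording only: the RII PHQ-9 is already planned for every consented participant, so no visit, measurement or change in sample size is needed. Reported within-arm improvement may be slightly smaller than it would be from the intake score.

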Research Design/Plan: We propose a randomized, double-blind, trial of TMS to the left dorsolateral prefrontal cortex (DLPFC) for patients with MDD all of whom at the patient's treatment clinic are concurrently receiving pharmaceutical and psychotherapeutic interventions. Subjects will undergo TMS treatments for at least 4 weeks, but the duration of their TMS treatments may be extended (e.g. up to 8 weeks of treatment) if approved by the subject's third-party insurance plan. Arm 1 delivers active rTMS to the left DLPFC using the standard aiming strategy. Arm 2 delivers active rTMS to the left anterior DLPFC using connectivity-based, image-guided aiming. Arm 3 delivers active rTMS to the left posterior DLPFC using connectivity-based, image-guided aiming. In all three arms, rTMS is administered in an image-guided, robotically-positioned TMS (iTMS) manner to ensure therapist blinding and equivalent subject experiences across arms. In all three arms, the following stimulation protocol will be used: 10 Hz iTMS delivered in 4 sec trains with 26 sec inter-train intervals, 37.5 minutes/session (i.e. 3,000 pulses/session), 5 sessions/week, for at least 4 weeks. Neuroimaging will be used both for treatment planning and to characterize any TMS-induced network plasticity using resting-state functional magnetic resonance imaging (rs-fMRI) at week 4 of each treatment arm. Clinical assessments will be administered weekly throughout treatment at the subject's treatment clinic. Additional psychological tests will be performed at UT Health—San Antonio's Research Imaging Institute (RII) at the baseline and post-treatment visits in order to track subject progress.

Clinical Relevance: This will be the first study to determine the clinical effects of connectivity-guided iTMS in the treatment of MDD, to provide clues about the ideal neural networks (anterior DLPFC vs. posterior DLPFC) to target for more robust clinical outcomes, and to identify potential biomarkers of treatment response including changes in brain networks connectivity.

Item 3 Background	

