For each subject, one of three left DLPFC treatment target locations will be determined (according to their randomization group): 1) 5-cm (e.g. standard of care) aiming to the left DLPFC brain region with the coil oriented towards the subject's nose; 2) connectivity-based aiming to the left, anterior (nearer the front) DLPFC brain region with the coil's E-field aligned according to the cortical column cosine model at the target site; 3) connectivity-based aiming to the left, posterior (nearer the back) DLPFC brain region with the coil's E-field aligned according to the cortical column cosine model at the target site. Stimulation intensity will be delivered in the same fashion as other TMS treatment trials for MDD: 120% of the subject's resting motor threshold (which was obtained at the Baseline MRI visit).

irTMS Position/Holding. For each subject, the coil pose will be pre-computed from structural and functional MRI (above) and stored as an individualized treatment plan. Each subject's treatment plan will be registered to his/her head by creating a scalp model with a high-resolution digitizer, an integrated component of the irTMS system. In each arm, the TMS coil will be positioned and held by the robot (under the TMS treatment technician's supervision).

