irTMS Treatment Sessions. All participants will continue with their TAU at the subject's treatment clinic including regular medication management, encounters with their attending psychiatrist, and therapy sessions. An effort will be made to limit the disruptions in subjects' TAU by working research assessments and irTMS treatment sessions around their expected TAU programming. irTMS treatment visits will take place at their treatment clinic starting as soon as possible after the treatment plan is completed, expected to be 1-10 working days following baseline scanning. At the respective TMS treatment target site, the treatment clinician's team will deliver rTMS using the FDA-approved rTMS treatment protocol for MDD. This TMS protocol consists of 4 seconds of 10 Hz rTMS followed by a 26 second rest period; the treatment lasts for a total of 37.5 minutes (e.g. 3,000 rTMS pulses/session). Treatment is 5 days per week for at least 4 weeks in all arms. All treatments will delivered using a liquid cooled figure-8 MagPro coil (MagVenture, Denmark). If study participants decide that they cannot tolerate the prescribed dose of irTMS (e.g. 120% of resting motor threshold), they will be withdrawn from the study (see Discontinuation and Withdrawal of Patients Section below).

Phase II: Post-Treatment Follow-Up

Post-treatment MRI. Immediately following the last irTMS treatment at the end of the 4th week, a second functional MRI scan will be conducted to assess treatment effects. The post-MRI will occur any time after last treatment with up to a 3-day window for completion. After the post-treatment MRI session, each subject will also undergo another brief motor threshold assessment in order to document any changes—which may be used to report on the safety of this TMS treatment protocol. This second scanning visit should take approximately 1 hour.

Participant Blind Form. The Participant Blind Form measures the participant's best guess about the study treatment that they received, level of confidence in this guess, and how unblinding could potentially have occurred. This form will be used at treatment completion and follow-up for all of the RII's double-blind irTMS studies.

Independent Evaluator Blind Form. The Independent Evaluator Blind Form measures the independent evaluator's best guess about the study treatment that the subject received, level of confidence in this guess, and how unblinding could potentially have occurred.

Phase III: 1 Month/3 Month Follow-Up

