One month and three months after the final irTMS treatment session, participants will be interviewed (either in-person or over the telephone) by a member of the research team. Results from these assessments will be stored on the RII's secure XNAT server..

Table of Study Procedures:

Phase	Pre-Study			TMS Treatment Phase (at the clinic & the RII)				Post-Treatment (at the RII)	1 Month/ 3 Month Follow-Up (in-person or via telephone)
	Clinic Intake	Baseline	MRI Appt	Wk 1	Wk 2	Wk 3	Wk 4	Wk 5	Wk 8/Wk16
Review Medical History	X								
Informed Consent		X							
Metal Screening		X							
Patient Health Questionnaire-9 (PHQ-9)		X		X	X	X	X	X	X
Montgomery-Ashberg Depression Rating Scale (MADRS)			X					X	X
Adverse Events Monitoring			X	X-X	X-X	X-X	X-X	X	X
Concomitant Medications/Treatment		X		X-X	X-X	X-X	X-X	X	X
Structural MRI			X						
Intrinsic Connectivity by Blood- Oxygen-Level-Dependent Functional MRI			X					X	
Motor threshold assessment			X					X	
irTMS Treatment (at least 20 weekdays)				X-X	X-X	X-X	X-X		
Participant Blind Form							X		
Independent Evaluator Blind Form							X		

Data Protection. Data will be coded using an assigned number. Data collected during treatment will be placed into locked cabinets at the subject's treatment clinic's offices. Every member of the research team will be trained and monitored about how to handle and protect both medical and research records. Furthermore, the research team strictly controls access to study data. No identified data (either copies or originals) will be maintained at the study site. The study site will maintain a list of assignment numbers for the purpose of linking subsequent research materials.

Risk/Benefit Assessment.

Risks and Side Effects related to the irTMS applied to Dorsolateral Prefrontal Cortex Brain Region:

- Likely, some may be serious. In 100 people, approximately 20-30 may have:
 - Mild headache
 - Scalp and/or Facial pain/discomfort
 - Scalp and/or Facial Muscle Twitching
 - Neck pain
- Less Likely, some may be serious. In 100 people, approximately 5-10 may have:
 - Dizziness
 - Sleepiness
- Rare and Serious. In 100 people, approximately 1-2 may have:
 - Seizures

Risks and Side Effects related to the Robot placement of the irTMS include those which are:

- Rare and Serious. In 100 people, approximately 0-1 may have:

- Physical injury from the robotic device.

Risks and Side Effects related to the MRI include those which are:

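### Neither stated basis for operator blinding hides the coil's final site and angle from staff who receive the plan and supervise placement, and the blind check leaves those staff out

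*Combined protocol and SAP*

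**What the plan says.** Two bases for operator blinding are given.

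- **Locked list.** Item 6, Random Assignment, says the master list "will not be available to members of the research team until all of the participant's treatment sessions and symptom assessments have been completed". The next sentence opens with *therefore* and concludes that all members of the clinic's "irTMS treatment team will be blinded to which treatment arm each participant is assigned".
- **Robotic delivery.** Items 2 and 4 say that all three arms use image-guided robotic delivery, in a "manner to ensure therapist blinding and equivalent subject experiences across arms".

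The same documents describe what the operators handle and see.

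- Random Assignment says that an individual plan is made for each participant, "which will be securely-transmitted to the irTMS treatment team" at the clinic.
- irTMS Position/Holding says that this plan stores the pre-computed coil pose. For delivery, "the TMS coil will be positioned and held by the robot (under the TMS treatment technician", and the sentence goes on to give that technician supervision of the robot.
- irTMS Treatment Planning makes the target depend on the randomisation group. The standard arm uses the 5-cm site with the coil pointing to the nose. The other two arms use an anterior or a posterior site, with the coil's "E-field aligned according to the cortical column cosine model at the target site".

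Item 6 defines two blind forms. For the Participant Blind Form it says "This form will be used at treatment completion and follow-up". For the "Independent Evaluator Blind Form" the text gives no timing. There is no form for operators. The Table of Study Procedures marks both forms once, at Wk 4.

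**The concern.** A locked list stops staff from looking up the allocation. It does not blind staff who are sent the product of that allocation and watch it being applied. If the coil pose can be read, the operators could infer the arm without ever opening the list.

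The risk has a direction. All arms are active, but the hypotheses in Item 4 are ordered (anterior over posterior over standard), and Item 2 describes the standard targeting as unsophisticated. It also has a route. The PHQ-9 is part of the primary outcome and is collected weekly during treatment. Item 4 places the weekly assessments at the treatment clinic, where medication management and therapy also run. Nothing separates the weekly assessment from the irTMS team. Operators see each participant on every treatment day and could pass on expectation or mention coil position to treating clinicians.

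The trial could then report a double-blind comparison with no data on the staff who have the most direct view of the intervention.

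**Working it through.** The documents give no figure for blinding to reproduce, so the check is mainly a comparison of sections, with some arithmetic for scale.

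**1. What each basis hides**

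| Basis | What it hides | What it leaves open |
|---|---|---|
| Locked master list | The recorded allocation | The plan generated from it, which is sent to operators |
| Robotic delivery in all arms | Differences in procedure; the need for manual aiming | The coil's final site and orientation |

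No section describes masking of the plan or the operator's display, or bars operators from outcome assessment.

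**2. How the pose is set (irTMS Treatment Planning)**

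| Arm | Site | Orientation |
|---|---|---|
| Standard | 5-cm rule | Toward the nose, same rule for all |
| Anterior | Connectivity-based, nearer the front | Individual, cosine model |
| Posterior | Connectivity-based, nearer the back | Individual, cosine model |

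Site and orientation are therefore both potential cues. Nose-pointing can be judged without knowing the hand motor spot.

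**3. Exposure**

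Item 6 gives 66 randomised and 50 expected completers per arm, and at least 20 sessions each.

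- Randomised: 66 × 20 = 1,320 scheduled supervised sessions per arm.
- Completers only: 50 × 20 = 1,000 per arm.

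These counts measure opportunity to observe. They are not estimates of unblinding or bias.

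**4. Timing of the blind check (Table of Study Procedures)**

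| Item | Marked at |
|---|---|
| Participant Blind Form | Wk 4 |
| Independent Evaluator Blind Form | Wk 4 |
| MADRS | MRI appointment, Wk 5, Wk 8/Wk 16 |
| PHQ-9 | Baseline, Wk 1 to Wk 5, Wk 8/Wk 16 |

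The evaluator's single guess precedes 3 of 3 post-baseline MADRS visits (Wk 5, 8 and 16). Unblinding that arises at or after those ratings would not be recorded. The participant form has no follow-up mark, although the text calls for one. Item 2 allows treatment for up to 8 weeks, so Wk 4 is not treatment completion for extended courses.

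**5. Would an operator form be informative?**

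Assumptions, none from the documents: one guess per subject, independent guesses, chance rate 1/3, one-sided level 0.025. The cut-off is the smallest r with P(X ≥ r | n, 1/3) ≤ 0.025.

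| Guesses | Cut-off | Exact tail | Power if true rate is 40% | 45% | 50% |
|---|---|---|---|---|---|
| 150 | 62 (41.3%) | 0.0245 | 0.40 | 0.84 | 0.99 |
| 198 | 80 (40.4%) | 0.0221 | 0.48 | 0.92 | 0.997 |

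In a hypothetical case where orientation always separates standard from connectivity arms, and anterior versus posterior is a coin toss, the expected correct rate is 1/3 × 1 + 2/3 × 1/2 = 67%, well above either cut-off. One operator will treat many subjects, so guesses will be correlated and real power will be lower. The documents do not give the number of operators.

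**The case against.** The case on the other side is substantial.

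- **Recognition is not shown.** All targets lie in left DLPFC. Motor threshold, and with it the hand spot, is obtained at the baseline MRI visit, so clinic operators may have no reference for a 5-cm offset. Cosine-model orientation varies by subject and may sometimes lie near nose-pointing. Anatomy may blur anterior and posterior. No section says that the plan carries an arm label or what the display shows.
- **Operators are not named as raters.** The table places the Wk 5 visit, where MADRS is rated, at the imaging institute, away from the clinic.
- **A Wk 4 evaluator guess is defensible.** A guess taken before the outcome rating is less contaminated by perceived improvement. The gap may be only days, since the post-treatment scan has a window of up to 3 days.

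All of this stands, and it limits the point to potential unblinding. A reader might infer that operators will know the arm, or that the evaluator form is simply at the wrong visit. The documents support neither. Nor do they support treating MADRS as the only clinician-rated scale after baseline: Item 4 mentions clinician-rated scales among the weekly assessments, while the table lists only the PHQ-9 in those weeks.

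The objection does not supply any masking of the plan or display, a rule separating operators from weekly assessment, or any data on operator guesses.

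**Conclusion.** The point holds as a gap in the blinding argument and in its check. The conclusion under Random Assignment does not follow from a locked list. Robotic delivery equalises the procedure without hiding the final site and angle. The plan is potentially arm-revealing for every randomised subject, no masking is described, and the forms as scheduled cannot show whether operators were blind.

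The only outright contradiction is the participant form: the text has completion and follow-up, the table has Wk 4 only. For the evaluator form, the gap is the lack of a later repeat.

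No size of bias can be derived from the documents, and none is claimed. The conclusion assumes that operators can see the coil they supervise, and that the independent evaluator, whose role is not defined, rates the MADRS. No sample size or analysis changes. What changes is how far the trial can claim, and document, double blinding. This should be corrected, but it does not prevent the trial from running.

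**What to change.** 1. Reword the conclusion under Random Assignment: participants and outcome evaluators are kept blind, and operators are treated as potentially unblinded.
2. Send the plan under study code with the coil pose and the scalp-model registration data that delivery needs, but with no arm label or connectivity map.
3. Have participants complete the weekly PHQ-9 themselves without operator involvement. State that no operator acts as an outcome rater, and bar operators from discussing coil position with participants, raters or treating clinicians.
4. Have operators complete the existing blind form at the end of each subject's treatment.
5. Keep the Wk 4 evaluator form and repeat it at the last follow-up MADRS. A repeat fixed at Wk 5 would fall mid-treatment for extended courses.
6. Reconcile the table with the text by placing the participant form at actual treatment completion and at follow-up.

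Record guesses by target name. Arm numbers in Aim 1 (anterior 1, posterior 2, standard 3) differ from those in the arm descriptions (standard 1, anterior 2, posterior 3) and must be reconciled before guesses are coded.

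The cost is protocol wording, a few extra uses of an existing form, and a handling rule for a self-report questionnaire. The downside is a weaker double-blind claim for operators.
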